-Due to power limitations we will restrict the number of covariates/independent variables to eight (10 patients/independent variable)(63). Based on suspected prognostic factors for LBP disability (61, 62) and suspected factors associated with serum cytokine levels (64, 65), we will add the following as covariates into the model due to possible confounding: age, leg pain (0-10 NRS), fear avoidance, emotional distress (dichotomized into HSCL-25 $\geq 1,75$ and $< 1,75$), psychiatric comorbidity (yes/no), other specific comorbidity (numerical, one point for each of rheumatoid arthritis, osteoarthritis, Diabetic, Cardiac/pulmonary) and sick leave (categorized into 1. working full time, 2. partial sick leave and 3. complete sick leave / disability pension / unemployed / student/other/unknown). Age, leg pain and fear avoidance will be continuous variables.

For each model we will evaluate:

1. The predictiveness by comparing the multiple correlation coefficient R^2 of the complete model with the R^2 in the model without the independent variable of interest (66).
2. The effect size described in terms of relative change in RMDQ. We will consider effect size $>30\%$ as clinically relevant, which equates approximately to a difference of 4 out of 12.8 (at baseline) RMDQ points.

The following models (1, 2A, 2B, 3, 4A, 4B, 5A, 5B, 5C, 5D, 5E) will differ in choice of independent variable of interest, which will be:

1. Cytokine category group based on cytokine classification group (4 categories of patients, figure 2). Each category of patients will be assessed versus the three other categories combined.
2. Classification variable defined by a Recursive Partitioning analysis using RPART command in R. Relative change in RMDQ from baseline to one-year follow-up will be dependent variable. Only patients nonmissing values in both baseline and one-year follow-up RMDQ score will be included. Stopping conditions will be $\text{maxdepth}=3$ and n_{min} (minimal number of observations in terminal/leaf node)=5. We will use tenfold cross-validation and a complexity parameter of 0,01. We will perform two Recursive Partitioning models that differs only in what variables that are included:

Statistical Analysis Plan for analysis of cytokines as prognostic factors and predictors of antibiotic treatment effect in patients with chronic low back pain and Modic changes (the AIM trial) - - version 1.0

- A. all 39 cytokines

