- B. all 39 cytokines, age, leg pain (0-10 NRS), fear avoidance, emotional distress, psychiatric comorbidity (yes or no), physical workload, and sick leave.
In models 2A and 2B we will use cytokine variables as categorical with cutoffs at -2, -1.5, -1, -0.5, 0, 0.5, 1, 1.5 and 2 SD above the mean in the healthy control groups, and other variables as defined for the linear regression analyses above. Physical workload will be categorized into 1. mostly sitting, 2. job requires a lot of walking and 3. job requires a lot of walking and lifting / job requires physically heavy work.
3. Abnormal cytokine values, based on PCA analysis of healthy controls and patients with MCs (figure 3), dichotomized into normal (inside yellow circle) and abnormal (outside yellow circle) cytokine levels.
4. Principal component 1 (continuous variable) from
 - A. PCA analysis 3A of cytokines as predictors of treatment effect
 - B. PCA analysis 3B of cytokines as predictors of treatment effect
5. Individual cytokines categorized with cutoffs at 0, 1 and 2 SD above the mean in the healthy control groups
 - A. MIF levels
 - B. TNF α levels (67)
 - C. IL-6 levels
 - D. IL-8 levels
 - E. IL-1 β levels

For model 2B we will avoid adding any covariate that is also used to define the independent variable of interest. E.g. if the recursive partitioning model define the independent variable based on age and leg pain, we will exclude age and leg pain as covariates in the final linear regression model.

For all models a sample size (n=78) will, assuming an R^2 of 30% in the incomplete model including seven known prognostic factors but without the one independent variable of interest (estimates of R^2 in models excluding baseline values are 20-30% (68, 69)), give a power ($\alpha=0.05$, $\beta=0.2$) to detect increases of 7% (absolute percentage points) in R^2 in the complete model with one variable of interest and seven covariates (using the 'power rsquared' function in Stata). For model 1, detecting a difference of 30% in change from baseline RMDQ (SD 5) between two groups of n=28 and n=44 will give a power ($\alpha=0.05$) of 90% (using the 'power oneway' function in Stata).

Table 3 – Main analyses of cytokine-defined prognostic factors

| Hypothesis and rationale | Variables and subgroups | Analysis |
|---|--|------------|

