Assess other possible confounders (not included in main analyses due to power limitations):

We will perform a sensitivity analysis for the main analysis (1, 2A and 2B), with the same statistical model but only including covariates with statistically significant beta coefficient in the corresponding main analysis, and depending on available number of further covariates (given maximum eight), the

Statistical Analysis Plan for analysis of cytokines as prognostic factors and predictors of antibiotic treatment effect in patients with chronic low back pain and Modic changes (the AIM trial) - - version 1.0

following covariates will be considered: treatment group (amoxicillin/placebo), comorbidity, NSAIDs use (at baseline and one-year follow-up), physical workload, sleep disturbance(64), BMI, smoking, LBP intensity at baseline (0-10 NRS), and prior surgery for disc herniation. Each sensitivity analysis will be compared to their respective main analysis by assessing R^2 .

The following sensitivity analyses will be considered performed:

Assess the possibility of non-linear effects of the cytokine

For each main analyses 5 (A-E), we will consider using a correspondent multivariable fractional polynomial (MFP) model or other polynomial regression model (73). All covariates of the original regression analyses will be forced included (by setting nominal p-values for variable selection to one in MFP model), only the independent variable of interest will be tested for a non-linear relationship (degrees of freedom for other continuous variables will be set to one) with (for MFP) standard powers (-2, -1, -0.5, 0, 0.5, 1, 2, and 3) and a fractional polynomial election significance level of 5% (using the mfp command in Stata). Each MFP model will be compared to its respective main analysis by assessing R^2 .

Independence of effect:

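### The 90% power given for prognostic model 1 is that of its most favourable contrast (category 1 has 56% on the same method), and the R² power given for all models cannot cover 2A and 2B

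*SAP*

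**What the plan says.** The SAP, under Analyses of cytokines as prognostic factors (hypothesis 2), Main analyses, ends its list of models with a power paragraph that makes two claims.

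- **Model 1.** "For model 1, detecting a difference of 30% in change from baseline RMDQ (SD 5) between two groups of n=28 and n=44" is said to give 90% power at alpha 0.05, using Stata's one-way ANOVA power function. The definition of model 1 in the same section reads: "Each category of patients will be assessed versus the three other categories combined". With four categories, that is four contrasts.
- **R² gain.** "For all models a sample size (n=78) will, assuming an R^2 of 30% in the incomplete model including seven known prognostic factors", give 80% power to detect a gain of 7 percentage points "in the complete model with one variable of interest and seven covariates". Models 2A and 2B are among the models covered. Their predictor is described as: "Classification variable defined by a Recursive Partitioning analysis using RPART command in R". The tree is grown on relative change in RMDQ, the outcome of the regression that follows, and only in patients with both RMDQ scores.

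The Statistical principles section promises a power calculation for the top-ranked pre-defined analysis of each hypothesis. For hypothesis 2 that is model 1.

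**The concern.** A single power figure is attached to a model that consists of four tests on groups of very different size. Table 5B has 8 patients in category 1 and 28 in category 2. A reader who sees a null result for category 1 could set it against 90% power that this contrast does not have, and take it as evidence of no association.

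The R² claim has a similar problem of scope. It assumes one pre-chosen variable and seven covariates. In 2A and 2B the number of leaves is not known in advance, the leaves are chosen on the outcome then tested, and 2B may drop covariates that the tree has used.

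For hypothesis 1 the SAP says openly that analysis 2 is underpowered at 4 points. For hypothesis 2 it names power limits only for the number of covariates and for the placebo-only analyses, not for the category 1 contrast.

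**Working it through.** **Inputs.** SD 5 and alpha 0.05 two-sided (power paragraph; Statistical principles). Difference of 4 RMDQ points, which the SAP equates approximately with 30% of a baseline mean of 12.8. Category sizes in complete cases from Table 5B, amoxicillin plus placebo: category 1, 5+3 = 8; category 2, 19+9 = 28; category 3, 13+6 = 19; category 4, 8+9 = 17; total 72.

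**Method for model 1.** Two-group one-way ANOVA, noncentral F with 1 and N−2 df, noncentrality λ = (d/SD)² × n1·n2/N. Here (4/5)² = 0.64 and N = 72.

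**The SAP's figure first.** 28 vs 44: λ = 0.64 × 1232/72 = 10.95, power 90.4%. The 90% reproduces. At exactly 30% of 12.8 (3.84 points) it is 88.0%.

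**All four contrasts, same method:**

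| Category vs rest | Split | λ | Power, 4 points | Power, 3.84 points |
|---|---|---|---|---|
| 1 | 8 / 64 | 4.55 | 55.7% | 52.4% |
| 2 | 28 / 44 | 10.95 | 90.4% | 88.0% |
| 3 | 19 / 53 | 8.95 | 83.9% | 80.9% |
| 4 | 17 / 55 | 8.31 | 81.1% | 77.9% |

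For 80% power, unadjusted, category 1 needs a difference of 5.3 points (5.33/12.8 = 42% of baseline).

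**Can covariate adjustment rescue category 1?** Divide λ by 1−R² of the covariates and remove 7 error df. (Removing 8, because sick leave has three levels, changes nothing at this precision.)

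- R² 30%, the value the paragraph assumes: λ = 4.55/0.7 = 6.50, power 70.9%.
- R² 20%, the low end of the SAP's own range: λ = 4.55/0.8 = 5.69, power 65.1%.
- Both assume that category membership is uncorrelated with the covariates. If the covariates explain a share ρ² of membership, λ is also multiplied by 1−ρ². With R² 30% and assumed ρ² of 10%, 20% or 30%, power is 66%, 61% or 56%.

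**Can imputation rescue it?** In Table 5A (n=78) category 1 still has 8 patients. For 8 vs 70, power is 56.2% unadjusted and 71.4% adjusted at R² 30% with no correlation.

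**R² claim, one tested parameter.** λ = n·ΔR²/(1−R²full), reduced-model R² 0.30, seven covariates. For n=78 and ΔR² = 0.07: λ = 78 × 0.07/0.63 = 8.67 on 1 and 69 df, power 82.7%; 80% is reached at 6.6 points. For n=72: power 79.5%, and 80% is reached at 7.1 points. The 7-point figure therefore holds for each model 1 contrast and for models 3, 4A and 4B.

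**R² claim, models 2A and 2B.** The formula needs a predictor fixed before the outcome is seen. To illustrate what happens otherwise, trees were grown on pure noise: 39 independent cytokines with the SAP's cutoffs, n=72, leaves of at least 5, complexity 0.01, no cross-validation pruning. The adjusted F test was then run on the same data. It rejected in about 75% of 150 runs with a single split and about 99% at depth 3. Pruning would lower these rates, but it would not make the nominal power figure meaningful.

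**The case against.** Several counter-arguments are fair.

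- *Nothing is miscalculated.* True. A reader might infer an arithmetic error, but both figures reproduce; only their stated scope is at fault.
- *The group sizes are on the page.* The paragraph names 28 and 44, and Table 5B lists every category. But it attributes the result to model 1 and does not say that one contrast out of four was used, or which.
- *The R² claim states its own condition of one variable of interest.* This disposes of most of the objection to it. What remains is that a claim for all models includes 2A and 2B.
- *Models 5A–E.* A reader might infer that the 7-point figure also fails here, because of "Individual cytokines categorized with cutoffs at 0, 1 and 2 SD above the mean in the healthy control groups", which makes four bands. The SAP does not support that. It does not state the coding, and one ordinal term would satisfy the claim. The cap, "Due to power limitations we will restrict the number of covariates/independent variables to eight", and the later check headed "Assess the possibility of non-linear effects of the cytokine" are both compatible with a single term.
- *Category 1 is not singled out for hypothesis 2.* Correct. A reader might call it central because Table 2 links categories 1 and 2 to raised TNF-α, IFN-γ and IL-10. That is the rationale for treatment effect under hypothesis 1; the hypothesis 2 rationale in Table 3 favours no category.
- *Interpretation rests on R² gain and effect size.* Largely so, and the analyses are exploratory. Significance is nevertheless claimed at 0.05, and a significant association triggers the independence analysis.

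**Conclusion.** The point stands as one of scope. The 90% is the unadjusted power for category 2 versus the rest in 72 complete cases. On the same basis categories 1, 3 and 4 have 56%, 84% and 81%. Only category 1 has a serious shortfall, and it stays below 80% on every basis examined.

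The adjusted 71% for category 1 should not be read as its expected power. It is an upper bound that needs covariates to explain 30% of outcome variance and to be unrelated to category membership. The SAP gives reason to doubt the second condition, since it chose covariates partly because they may be associated with serum cytokine levels. Nor should the result be read as model 1 being underpowered throughout: at 4 points the other three contrasts exceed 80% unadjusted.

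The 7-point R² figure is sound for one tested parameter and has no meaning for 2A and 2B.

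All the model 1 percentages inherit the SAP's own step of applying an SD of 5 RMDQ points to an outcome analysed as relative change. The effect is on the interpretation of exploratory analyses only.

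**What to change.** Change the wording of the power paragraph:

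1. Label the 90% as category 2 versus the rest, unadjusted, 72 complete cases, 4 points, SD 5.
2. Report unadjusted power for all four contrasts (56%, 90%, 84%, 81%). Give any adjusted figure as an upper bound with its assumptions stated.
3. State that category 1, with 8 patients, is underpowered at 4 points, so a null result there is not evidence of no association.
4. Limit the 7-point R² claim to models with one tested parameter (each model 1 contrast, 3, 4A and 4B), and claim no R² power for 2A and 2B.

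The cost is that the stated power becomes less favourable. No data, model or analysis changes.

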The sample size for the main trial results was calculated to assess the treatment effect separately in each MC type group (1/2). In each MC type group, the study was designed to detect ($\beta = 0.1$, two-sided $\alpha = 0.05$) a mean difference of 4 (SD 5) in the RMDQ score between the two treatment groups (amoxicillin or placebo) at one-year follow-up. In total 180 patients were actually included (intention to treat population), 118 in the MC type 1 group and 62 in the MC type 2 group (16).

The trial protocol gives further details regarding sample size calculation and trial methods (1).

The AIM trial showed a statistically significant – but not clinically important – effect of Amoxicillin in the type 1 MC group, but no effect in the in the type 2 MC group (16). Subgroup analyses indicated a clinically relevant effect in patients with MC related oedema on MRI STIR sequences/series (7) and possibly also a borderline clinically relevant effect in younger patients (aged < 40 years)(6).

Patients

Patients included in this present study were a selected group with as ‘pure’ MC types as possible, who gave consent to participate in the AIM trial, and who provided blood samples and underwent MRI prior to enrolment. Of those selected 78 subjects were eventually randomized and took part in the AIM trial, 6 subjects did not satisfy the AIM eligibility criteria and were not included in the AIM trial (figure 1).

The selection criteria for this present study were, firstly, that two study radiologists agreed that the MRI inclusion criteria of the AIM trial (52) were fulfilled (i.e., type 1 and/or type 2 MCs with height \geq 10% of vertebral body height and diameter > 5 millimeters existed at the level of a prior disc herniation (index level)). Secondly, that type 1 was the most extensive MC type at two or more index level endplates (categorized as MC1, n=47) or that type 2, but not type 1, existed at the index level (categorized as MC2, n=48). From this selected group we included 84 subjects (46 MC1, and 37 MC2) in the present study.

Controls

Statistical Analysis Plan for analysis of cytokines as prognostic factors and predictors of antibiotic treatment effect in patients with chronic low back pain and Modic changes (the AIM trial) - - version 1.0

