1. To evaluate whether certain profiles of serum cytokine levels predict any treatment effect of 3 months oral amoxicillin in patients with chronic low back pain and type 1 or 2 MCs at the level of a previous lumbar disc herniation (cytokines as predictors of antibiotic treatment effect)
2. To evaluate whether certain profiles of systemic serum cytokine levels provide added prognostic value over known prognostic factors in patients with chronic low back pain and type 1 or 2 MCs at the level of a previous lumbar disc herniation (cytokines as prognostic factors independent of treatment)

Hypotheses

For each objective (1 and 2 above), we made respective hypotheses that

1. Patients with a certain pattern of serum cytokine levels at baseline in the antibiotic group report a significantly lower RMDQ score at one-year follow-up than patients with the similar cytokine pattern in the placebo group
2. Serum proinflammatory cytokine levels are associated with change in RMDQ score from baseline to one-year follow-up, given known prognostic factors.

Statistical principles

All analyses described in this plan are considered *exploratory* in the sense that the present objectives were not described in the original protocol, and are performed after results for treatment efficacy in the main trial (5) and in clinical and radiological subgroups (6, 7) were available. Any additional analyses not described in this SAP will be identified as *post hoc* in the article. Some analyses are based on *pre-defined subgroups*, (e.g. defined in advance of analyses), others on *post-defined subgroups*, meaning that subgroups will be defined by a data-driven approach.

All outcomes are analysed for superiority of one intervention compared to the other (hypothesis 1) or of having compared to not having a prognostic factor (hypothesis 2). All relevant statistical tests will be 2-sided and the nominal p value will be reported. All confidence intervals presented will be 95% and 2-sided. The assumption of normal distribution will be checked by visual inspection of a QQ-plot.

Statistical Analysis Plan for analysis of cytokines as prognostic factors and predictors of antibiotic treatment effect in patients with chronic low back pain and Modic changes (the AIM trial) - - version 1.0

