Statistical significance is claimed on the significance level (alpha) of 0.05 (two-sided). We will not adjust the significance level due to multiple testing as these analyses are hypothesis generating (exploratory) in the sense that any evidence of predictors of treatment effect will need to be confirmed in future studies (54).

Statistically significant differences of < 4 RMDQ points will not be considered clinically relevant (52). We calculate power / sample size for the top ranked analysis of pre-defined subgroups for each hypothesis, as recommended by the PROGRESS framework (3) (details given below under the respective analyses).

All analyses will be carried out using software packages Stata and R, blinded to treatment group.

Analysis populations

We will perform all analyses of potential cytokines as prognostic factors and as predictors of treatment effect in the ITT population (n=78).

Baseline cytokine profiles

According to the cluster analysis described above subjects will be categorized by one of four cytokine profiles (figure 2).

Description of baseline characteristics

For analyses of predictors of treatment effect

In addition to the demographic and baseline characteristics given in the main report of the AIM trial (16), we will report for each treatment group number and percentages of patients with arthritis, osteoarthritis, diabetes, cardiac/pulmonary disease, psychiatric disease, self-reported sleep disturbance and STIR composite variables (groups 2 and 3 (7)). For each treatment group we will also report the distribution of the cytokine profile categories at baseline (Table 5). We will summarise categorical variables by numbers and percentages, and continuous variables by mean and SD (if normal distribution) or median and interquartile range (if skewed distribution). We will note the clinical importance of any imbalance in baseline data between the treatment groups without statistical testing.

For analyses of prognostic factors

The report on baseline characteristics for the paper on prognostic factors will describe for each prognostic factor variable of interest (i. – ii. In table 3) the same baseline characteristic as in the report on predictors of treatment effect, in each category of the prognostic factor.

Methods to handle missing data

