-Independence of effect: If the treatment effect (difference in RMDQ score at 1 year follow-up between antibiotic and placebo groups) are more than 4 RMDQ points in any of the main analyses 1(A, B, or C), 2(A), or 3(A or B) we will repeat the same analysis including interaction terms of all such relevant variables x treatment group, age (dichotomized as above or below 40 years) x treatment group and STIR composite variable x treatment group (without the individual covariates age and STIR composite variable) in the same regression analysis (59). Both age and STIR composite variable modified the treatment effect in our prior analyses.

Analyses of cytokines as prognostic factors (hypothesis 2)

For hypothesis 2, we define eleven main analyses (1, 2A, 2B, 3, 4A, 4B, 5A-E) of prognostic factors. These main analyses are ranked in order, from what we consider most to least likely to be prognostic factors (based on prior evidence and knowledge of cytokines).

Main analyses

We will perform linear regression models as main analyses that all will have the following in common:

-Relative change in RMDQ from baseline to one-year follow-up will be dependent variable. This differs from other analyses in the AIM trial (RMDQ at one-year follow-up was dependent variable) because we here consider it problematic to adjust for baseline RMDQ-score as it could induce bias (due to regression to the mean or horse-riding / collider problems) (60). Such adjustment could on the other hand also be highly desirable because baseline score is thought to be one of the most important predictors of future follow-up scores (61, 62). Our choice of dependent variable attempts to take the baseline value into account, while avoiding the possible problem related to adjusting for the baseline value.

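### The 90% power for prognostic model 1 is calculated on absolute RMDQ points, while the endpoint is relative change, whose SD the SAP never gives

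*SAP*

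**What the plan says.** All places are in the SAP.

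- **Analyses of cytokines as prognostic factors (hypothesis 2), Main analyses**, on what all main models share: "Relative change in RMDQ from baseline to one-year follow-up will be dependent variable". The text explains this as a deliberate departure from the other AIM analyses, which use the one-year score.
- **Same section, evaluation item 2.** An effect above 30% on the relative scale counts as clinically relevant, "which equates approximately to a difference of 4 out of 12.8 (at baseline) RMDQ points".
- **Same section, power paragraph before Table 3.** The model 1 scenario is "For model 1, detecting a difference of 30% in change from baseline RMDQ (SD 5) between two groups of n=28 and n=44". The result is 90% power at alpha 0.05, from Stata's one-way ANOVA power routine.
- **The AIM-trial, sample size.** The same SD appears for the one-year score in points: "a mean difference of 4 (SD 5) in the RMDQ score between the two treatment groups".
- **Hypotheses, number 2**: "Serum proinflammatory cytokine levels are associated with change in RMDQ score from baseline to one-year follow-up, given known prognostic factors". The word relative is absent here; the Main analyses section supplies it.

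**The concern.** The power sentence combines a relative effect (30%) with an SD that has no percent unit and equals the main trial's SD in RMDQ points. Relative change divides each patient's change by that patient's own baseline, so its SD depends on the spread of baseline scores as well as on the SD in points. Converting the effect at the mean baseline does not convert the SD.

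Model 1 is ranked first among the prognostic analyses, and Statistical principles undertakes to calculate power for the top-ranked pre-defined analysis under each hypothesis. If model 1 shows nothing, readers will weigh that result against a quoted 90% which belongs to a different outcome variable.

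**Working it through.** **Inputs from the SAP.** Group sizes 28 and 44; these match category 2 in Table 5B (19 + 9 = 28) against the rest (72 − 28 = 44). Alpha 0.05, two-sided (Statistical principles). Effect 30%, equated to about 4 of 12.8 points. SD 5. Covariate R² of 30%, with a cited range of 20–30% (power paragraph).

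**Not in the SAP.** The SD of relative change, the SD of baseline RMDQ, and the baseline to follow-up correlation.

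**Formula.** For two groups, one-way ANOVA power is P(F > F₀.₉₅) under a noncentral F with 1 and n₁ + n₂ − 2 df and noncentrality λ = (Δ/SD)² × n₁n₂/(n₁ + n₂). Here n₁n₂/(n₁ + n₂) = 28 × 44/72 = 17.11, with 70 error df.

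**Step 1: the SAP's figure.**
- 4 points, SD 5: λ = 0.64 × 17.11 = 10.95, power 0.904. This is the stated 90%.
- Exactly 30% of 12.8, which is 3.84 points, SD 5: λ = 10.09, power 0.880.
- 30 percentage points with SD 5 percentage points: λ = 36 × 17.11 = 616, power about 1.00. So the 5 cannot be on the percent scale.

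**Step 2: the analysed scale.** If every patient had a baseline of exactly 12.8, the relative SD would be 5/12.8 = 39%. With varying baselines it can be larger, because low baselines produce large percentages. The table gives power for a 30 percentage-point difference, 28 v 44. The adjusted column multiplies the SD by √(1 − 0.30), removes seven error df for the seven covariates, and takes cytokine category to be uncorrelated with the covariates.

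| SD of relative change | Unadjusted | Adjusted, R² 30% |
|---|---|---|
| 30% (assumed) | 0.98 | 0.998 |
| 35% (assumed) | 0.94 | 0.99 |
| 39% (5/12.8) | 0.88 | 0.96 |
| 45% (assumed) | 0.78 | 0.90 |
| 47% (assumed) | 0.74 | 0.87 |
| 50% (assumed) | 0.69 | 0.83 |
| 60% (assumed) | 0.53 | 0.68 |

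Power is 90% at an SD of about 37.8% unadjusted and about 45% adjusted.

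**Step 3: how far the SD could move.** I simulated integer scores with baseline mean 12.8, baseline SD 3–5, lowest admitted baseline 1, 4 or 6, and mean follow-up about 9.8. All of these except the mean of 12.8 are assumptions.
- If 5 is the SD of change: relative SD about 40–47%, unadjusted power about 0.73–0.86.
- If 5 is the SD of the one-year score, as in the main-trial calculation, with correlation 0.3–0.7: relative SD about 31–82%, unadjusted power about 0.32–0.98.

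The second reading falls on both sides of 90%.

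**The case against.** The strongest counter-argument is that the SAP discloses its conversion. It says openly that 30% is about 4 of 12.8 points, so a reader can see what was entered, and the gap between 0.904 and 0.880 is only the rounding of 3.84 to 4. This stands for the effect but not for the SD, which is never converted.

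A reader might go further and infer that 90% is simply too high, and that the SAP should print a ceiling of 88% or a range of 74–88%. The documents do not support that. They give no SD of relative change, and an SD of 35% already gives 0.94 unadjusted. The planned model also carries seven covariates: at the SAP's own R² of 30%, power is 0.87–0.96 for SDs from 47% down to 39%. On the imputed population of 78 the category 2 contrast is 29 v 49 (Table 5A), which gives 0.90 unadjusted at an SD of 39%. A printed ceiling of 88% would itself be wrong.

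Adjustment does not rescue the stated figure either. The 90% is an unadjusted calculation, and the same 4 points over SD 5 with R² 30% would give 0.97. Compared like with like, a relative SD of 39% or more still gives less than the points calculation.

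Two further objections limit the weight of the point. The analyses are declared exploratory on a fixed sample, and a separate power statement in terms of R² covers all the models, so no estimate or test changes. The wording of hypothesis 2 is a general statement that the Main analyses section makes specific; adding the word relative there would be editorial.

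**Conclusion.** The point holds as a scale error. The stated 90% is the power to detect a 4-point difference in absolute RMDQ score with SD 5, and no hypothesis 2 main model makes that comparison. For relative change the figure is unsupported, because the SD it needs is absent.

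It may be overstated. In the simplest case, equal baselines of 12.8, unadjusted power is 0.88, and it falls to 0.78 and 0.74 at assumed SDs of 45% and 47%. The direction remains open: the result depends on whether the true SD lies above or below about 37.8% unadjusted, or about 45% with covariates explaining 30% of the variance. The consequence is moderate: a quoted power figure for the leading prognostic analysis needs restating, but the analysis itself does not change.

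**What to change.** In the power paragraph before Table 3, recompute the model 1 power for a 30 percentage-point difference, using the SD of relative RMDQ change in the AIM main-trial data. Those data were available before this SAP was written; the SD can be pooled over arms and needs no cytokine data. State whether the figure is unadjusted or covariate-adjusted and, if adjusted, the R² used.

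If that SD is not used, label the 90% as unadjusted power for a 4-point difference in absolute RMDQ score (SD 5), and add power over a range of SDs of relative change, as in the table above. Do not replace the 90% with a fixed ceiling or range that rests on assumed SDs.

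The cost is one recomputation and a few words, and a stated power that may become less favourable. No extra patients or data collection are needed.
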